7.3.5 Clinical Evaluation

7.3.5.1 Physical Examination

A complete physical examination as per standard of care (rectal and vaginal examination not required) will be performed by the investigator or designee at screening and at the time points specified in the Schedules of Assessments ([Section 7.1](#)). The physical examination will include general appearance, including examination of the skin, spleen, and signs of extramedullary leukemia and respiratory, cardiovascular, musculoskeletal, and neurological systems.

The individual performing the physical examination will characterize their findings as either normal or abnormal. Abnormal physical examination findings found during screening should be reported on the Medical History eCRF. Abnormal physical examination findings found after the subject has received investigational product will be reported on the Event eCRF.

7.3.5.2 ECOG Performance Status

Subjects will be graded according to the ECOG Performance Status (see [Appendix F](#)).

7.3.5.3 Height Measurements

Height in centimeters should be measured without shoes at screening.

7.3.5.4 Weight Measurements

Weight in kilograms should be measured without shoes.

7.3.6 Vital Signs

The following measurements must be performed: systolic/diastolic blood pressure, heart rate, respiratory rate, and temperature. Record all measurements on the vital signs eCRF.

The subject must be in a supine position in a rested and calm state for at least 5 minutes before blood pressure assessments are conducted. If the subject is unable to be in the supine position, the subject should be in most recumbent position as possible. The position selected for a subject should be the same that is used throughout the study and documented on the vital signs eCRF.

The location for temperature measurement selected for a subject should be the same that is used throughout the study and documented on the vital signs eCRF.

7.3.7 Pulse Oximetry

Oxygen saturation will be measured using a standard pulse oximeter. The subject must be in a rested and calm state for at least 5 minutes before pulse oximetry assessments are completed.

7.3.8 Electrocardiogram Performed in Triplicate

The subject must be in supine position in a rested and calm state for at least 5 minutes before ECG assessment is conducted. If the subject is unable to be in the supine position, the subject should be in most recumbent position as possible.

Electrocardiograms should be performed in a standardized method, in triplicate, and approximately 30 seconds apart, prior to blood draws or other invasive procedures. Each ECG must include the following measurements: QRS, QT, QTc, RR, and PR intervals.

Electrocardiograms will be performed as follows:

- Three sets of baseline ECGs will be collected ≥ 30 minutes apart, with each baseline ECG in triplicate run consecutively (ie, < 30 seconds apart; 2 sets collected at screening, and 1 set collected pre-dose on day 1 [ie, total ≥ 9 ECGs])
- Triplicate ECGs at time points after dosing

Baseline is defined as predose assessments from cycle 1 day 1. The investigator or designated site physician will review all ECGs. Electrocardiograms will be transferred electronically to an ECG central reader for analysis per Amgen instructions. Once signed, the original ECG tracing will be retained with the subject's source documents. At the request of the sponsor, a copy of the original ECG will be made available to Amgen.

Standard ECG machines should be used for all study-related ECG requirements.

7.3.9 Clinical Laboratory Tests

The tests listed below in Table 15 will be conducted on samples collected and analyzed by standard laboratory procedures at the time points specified in the Schedule of Assessments (Section 7.1). The test results are to be recorded on the eCRFs. Missed test(s) that are not done must be reported as such on the eCRFs.

Table 15. List of Analytes

Local Laboratory					
Chemistry	Hematology	Urinalysis	Coagulation	Other Labs	Central Laboratory
Sodium	Hemoglobin	Specific gravity	PT	Pregnancy test ^a	[REDACTED]
Potassium	Hematocrit	pH	PTT	Serology (HepB, HepC)	Pharmacokinetics
Bicarbonate	Platelets	Blood	INR	Bone marrow assessments:	Pharmacogenetics sample
Or Total CO ₂	WBC total and Differential	Protein	Fibrinogen	-morphology	[REDACTED]
Chloride	Total Neutrophils	Glucose			[REDACTED]
Total protein	Seg. Neutrophils	Bilirubin			[REDACTED]
Albumin	Lymphocytes	Ketones			[REDACTED]
Calcium	Monocytes	Microscopic exam			[REDACTED]
Magnesium	Bands/Stabs	(performed at the discretion of the investigator)			[REDACTED]
Phosphorus	Eosinophils				[REDACTED]
Glucose	Basophils				[REDACTED]
BUN or Urea	Blasts				[REDACTED]
Creatinine	Absolute neutrophil count				[REDACTED]
Total bilirubin	Myeloblasts				[REDACTED]
ALP				Standard bone marrow	[REDACTED]
AST					[REDACTED]
ALT					[REDACTED]
Amylase					[REDACTED]
Lipase					[REDACTED]
CRP					[REDACTED]
LDH					[REDACTED]
Uric Acid					[REDACTED]
Ferritin					[REDACTED]
eGFR (per institutional formula)					[REDACTED]

ALP = alkaline phosphatase; ALT = alanine aminotransferase; anti-HBc = Hepatitis B core antibody; AST = aspartate aminotransferase; CRP = C-reactive protein; HepBsAg = hepatitis B surface antigen; HepCAb = hepatitis C antibody; INR = international normalize ratio; LDH = lactate dehydrogenase; MCV = mean corpuscular volume; [REDACTED]; PT = prothrombin time; PTT = partial thromboplastin time; WBC = white blood cell
^a Serum pregnancy test will be performed for all females unless surgically sterile or > 2 years postmenopausal.

Approved

Additional procedures (eg, collection of an unscheduled blood sample to measure cytokine levels) deemed necessary as part of standard of care or as required by local laws and regulations may be performed at the investigator's discretion.

A serum pregnancy test will be performed locally at each site on all females unless they are surgically sterile or > 2 years postmenopausal. On visits where required, the serum pregnancy test must be performed prior to dosing with investigational product. If the pregnancy test is positive at day 1 of cycle 1, the subject should not be given investigational product.

7.3.10 Events

Adverse event and serious adverse event as well as disease-related event assessments will be made throughout the study and will be evaluated and recorded in the source documents and on the eCRF as specified in [Sections 9.2](#) and [9.1.1](#), respectively. The severity of all events will be graded according to CTCAE, version 4.0 ([Appendix A](#)) unless specified otherwise. **Exception:** CRS will be graded according to the adopted grading system referenced in ([Lee et al, 2014](#), see [Table 5](#)).

7.3.11 CT Scan or MRI Cranial

A CT scan or contrast-enhanced magnetic resonance imaging (MRI) of the head should be considered for subjects who experienced a CNS event Grade 3 or higher, particularly in cases of confusion, disorientation or seizures.

7.3.12 Pharmacokinetic Blood Sampling

[figure not shown]
Blood samples will be obtained for determination of serum concentrations of AMG 673 at the time points specified in the Schedules of Assessments ([Section 7.1](#)) Blood must not be drawn from the port catheter during IP infusion and 5 minutes after end of infusion. If a permanent central line with more than 1 lumen is used, blood draws can be done via the lumen that is not used for drug administration. However, the preference is for PK samples to be drawn peripherally during infusion. If the PK sample must be drawn through the central line, AMG 673 administration should be interrupted during sample withdrawal. A 5-minute waiting time is recommended before PK sampling.

Sample collection, processing, storage, and shipping instructions are provided in a separate laboratory manual.

[figure not shown]

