6.2.1.1.3 Schedule A and B

Up to 12 treatment cycles can be administered to each subject as long as the subject is deriving benefit in the judgment of the investigator.

If the next higher dose is deemed reasonably safe by the DLRT, intra-subject dose escalation is allowed (see [Section 3.1](#)) and additional hospitalization and procedures are required (see [Section 7.2.2](#)).

Additionally, subjects will be hospitalized for a minimum of 72 hours under the following circumstances:

- after each dose step, if applicable
- after dose increase in case of intra-subject dose escalation

Subjects will be hospitalized for a minimum of 48 hours under the following circumstances:

- after re-start of treatment after an interruption due to adverse event

Approved

Subjects can be hospitalized for a longer time period at the discretion of the investigator. A nurse trained in emergency medicine or a physician must be available when the infusion of AMG 673 is started for immediate intervention in case of complications. The hospitalization period may be extended at the discretion of the investigator. During hospitalization periods, an immediately accessible emergency room with resuscitation equipment must be available.

Prior to hospital discharge, vital signs will be measured in order to detect possible signs and symptoms of cytokine release syndrome. If required for logistical reasons (eg, long travel times), subjects may be hospitalized the day before start of dosing (day -1) of any cycle for required PK samples.

The start time of infusion should be chosen carefully so as to avoid any interference or inconvenience with time points of safety assessments or PK/PD measurements. The site should record any unscheduled interruption of an infusion on the eCRF, and provide the start and stop date/time of the infusion.

AMG 673 should be administered through a central venous access at a constant flow rate. The drug should not be administered as a bolus. In the event that administration through a central venous access is not possible, AMG 673 may be administered through a peripheral venous line. The IPIM will have further information regarding drug preparation and administration for AMG 673.

The quantity administered, start date/time, stop date/time, and lot number of IP are to be recorded on each subject's eCRF.

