7.2 General Study Procedures

A signed and dated IRB/IEC approved ICF must be obtained prior to performing any study-specific procedures including discontinuing standard therapy for observing a study washout period.

During the study, every effort should be made to perform the study procedures as indicated on the Schedules of Assessments ([Section 7.1](#)). In case of a new dose step (ie, subject receives a dose in a later cycle that they have never received before), cycle 1 assessments apply.

Subjects will be seen in the clinic for study evaluations. When electrocardiograms (ECGs), vital signs, blood sample collections, biomarker sample collections, and aspirate/biopsy sample collections occur on the same visit, ECGs and vital signs should be performed before samples (blood, biopsy/aspirate) are collected. Blood samples must not be taken/drawn from the catheter port used for AMG 673 infusion. If a permanent central line with more than 1 lumen is used, blood draws can be done via the lumen that is not used for drug administration (see also [section 7.3.12](#)). The time of blood sample collection must be recorded with the exact time of collection (do not use the time that the samples were frozen or any other time point). For blood samples scheduled on the day of an infusion, the blood sample should be taken prior to infusion start unless indicated otherwise in the schedule of assessments.

The study specific manuals provide additional details regarding the requirements for these procedures.

Acceptable deviation windows are as follows (any greater deviations require the sponsor approval):

- Dose time \pm 10 minute window.
- ECGs, biomarker blood draws (cycles 1 – 3), vital signs (incl. pulse oximetry):
 - \pm 15 minute window if collected within the first 24 hours (excluding the 24 hour sample) after the start of an infusion (or dose step, if applicable).
 - \pm 2 hour window if collected between 24 hours and 3 days after the start of an infusion.
 - Assessments after day 3 post infusion start should be performed on the indicated study day, but not at a certain hour of the day.
 - \pm 1 day window if collected 1 week after infusion start or later, or at the EOI.
- Bone marrow assessments post treatment start: \pm 3 days

- PK blood draws in cycles 1 - 3:
 - within 2 hours prior to infusion start
 - \pm 15 minute window for samples taken within the first 24 hours after start of each infusion and within 24 hours after EOI for each infusion.

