10. STATISTICAL CONSIDERATIONS

10.1 Study Endpoints, Analysis Sets, and Covariates

10.1.1 Study Endpoints

[figure not shown]
Primary Endpoint:

- Safety: subject incidence and grade of adverse events and dose limiting toxicities (DLTs)

Secondary Endpoints:

- Pharmacokinetic parameters including, but not limited to: half-life, maximum observed concentration (C_{max}), minimum observed concentration (C_{min}), area under the concentration-time curve from time 0 to the time of the last quantifiable concentration (AUC_{0-last}) and clearance (CL) of AMG 673
- Efficacy parameters: response rate (response defined as CR/CRi/morphologic leukemia-free state [per modified IWG criteria] or CRh*), duration of response, time to progression, time to response

Exploratory Endpoints:

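### Protocol Sections 7.2 and 7.3.12 give different rules for drawing blood from the line that carries AMG 673, and a single-lumen site can follow one while breaching the other

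*Protocol*

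**What the plan says.** Section 7.2 of the protocol (General Study Procedures) is unconditional: "Blood samples must not be taken/drawn from the catheter port used for AMG 673 infusion". For a permanent central line with more than one lumen it permits draws from the lumen that does not carry the drug, and it refers the reader to Section 7.3.12.

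Section 7.3.12 (Pharmacokinetic Blood Sampling) puts a time limit on the ban: "Blood must not be drawn from the port catheter during IP infusion and 5 minutes after end of infusion". It repeats the other-lumen route and says that "the preference is for PK samples to be drawn peripherally during infusion". It then adds a fallback: "If the PK sample must be drawn through the central line, AMG 673 administration should be interrupted during sample withdrawal", followed by "A 5-minute waiting time is recommended before PK sampling". The fallback does not say which lumen is meant. Collection and processing instructions are left to a separate laboratory manual.

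Central dosing is the default. Section 6.2.1.1.3 says: "AMG 673 should be administered through a central venous access at a constant flow rate", with a peripheral line as the alternative when central access is not possible. Section 10.1.1 makes PK a secondary endpoint: "Pharmacokinetic parameters including, but not limited to: half-life, maximum observed concentration" and, further on in the same list, Cmin, AUC0-last and clearance.

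**The concern.** The two sections govern the same act and cross-refer, but they do not state the same rule. A site with a single-lumen central line, dosing centrally as directed, has no permitted central draw under 7.2. Under 7.3.12 it can pause the infusion and sample, or wait more than five minutes after the end and sample, in both cases through the line that has just carried the drug.

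Drug left in that line would push the measured concentration upward. The exposed samples are those during and shortly after infusion, so Cmax and the early part of AUC would be too high and clearance too low, and only in subjects sampled this way. Cohorts have 3 to 4 subjects, and SAP Section 9.7.1 summarises PK by dose level with means and standard deviations, so one affected subject would carry weight. Neither document asks for the draw site to be recorded, so an affected sample could not be recognised from the study data.

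**Working it through.** No figure in the plan bears on this point, so the main check compares the two sections.

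| Situation | Section 7.2 | Section 7.3.12 |
|---|---|---|
| Drug port, infusion running | Forbidden | Forbidden |
| Drug port, more than 5 minutes after the end | Forbidden | Outside the stated ban, so allowed by implication |
| Other lumen of a multi-lumen line | Allowed | Allowed |
| Central line with infusion paused, lumen not named | Allowed only from the other lumen | Allowed; wait of 5 minutes recommended |
| Peripheral vein | Allowed | Preferred during infusion |

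The rows conflict only where the drug lumen is the draw lumen.

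**Are scheduled samples affected?** Yes. Infusions last about 30 minutes to 3 hours (Sections 6.2.1.1.1 and 6.2.1.1.2). Tables 10 and 11 mark PK samples on days 12 and 19 for the end of infusion. In cycles 1 to 3, Section 7.2 allows PK samples a window of plus or minus 15 minutes. A sample taken from the drug port between 5 and 15 minutes after the end is therefore on time and outside the 7.3.12 ban, but breaches 7.2.

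**How large could the error be?** This is an illustration only.

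Inputs from the documents:
- A 0.05 µg dose is predicted to give a maximum serum concentration of about 0.016 ng/mL (Section 2.4).
- Compatibility of administration systems was tested at 100 and 5000 ng/mL (summary of changes for Amendment 2). These are test concentrations, not the stated concentration for any dose.

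Assumptions:
- Cmax scales linearly with dose.
- The concentration in the line lies between the two tested values.
- 10 µL of solution is carried into a sample of 2 to 5 mL.

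Predicted Cmax: 0.05 µg / 0.016 ng/mL = 3.125 L, and 72 µg / 3.125 L = 23.04 ng/mL.

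Added concentration = line concentration × carried volume / sample volume:

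| Line (ng/mL) | Sample (mL) | Added (ng/mL) | Share of 23.04 ng/mL |
|---|---|---|---|
| 100 | 5 | 100 × 0.01 / 5 = 0.2 | 0.9% |
| 100 | 2 | 100 × 0.01 / 2 = 0.5 | 2.2% |
| 5000 | 5 | 5000 × 0.01 / 5 = 10 | 43.4% |
| 5000 | 2 | 5000 × 0.01 / 2 = 25 | 108.5% |

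Varying the carried volume from 1 to 50 µL widens the range at 72 µg to about 0.1% to 543%. At the 108.5% corner, one such subject among three raises the cohort mean by 108.5 / 3 = 36%.

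That corner is demanding. At 5000 ng/mL the whole 72 µg dose would occupy 72,000 / 5000 = 14.4 mL; at 100 ng/mL it would occupy 720 mL. The documents give no infusion volume for this dose.

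**The case against.** The best defence reads 7.3.12 in sequence. It names the other lumen, then prefers a peripheral draw, then says to pause if the central line must be used. Read that way, the pause is an added precaution for a draw from the other lumen, and the two sections agree. Sites that obey the stricter 7.2 never breach 7.3.12, and the documents do not say how many subjects have single-lumen lines. This stands for multi-lumen lines. It does not settle the single-lumen case, where there is no other lumen, and it does not explain why the port ban has a time limit in one section and none in the other.

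Several stronger readings are tempting, but the documents do not support them:

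- *The protocol expressly permits port draws five minutes after infusion.* It does not. The permission is only implied by the time limit.
- *PK results are contaminated.* Nothing shows this. The laboratory manual may require flushing or discarding, and the illustration runs from negligible to large on assumed inputs. At 100 ng/mL the line holds only about four times the predicted serum peak.
- *Pausing the infusion violates a constant-rate requirement.* Section 6.2.1.1.3 says the rate should be constant, and the same section provides for recording unscheduled interruptions. SAP Section 9.7.1 uses actual dosing and sampling times. This is secondary at most.
- *Dose escalation is distorted.* The model recommendation rests on DLTs (Section 10.3.1). PK is one of many inputs that the DLRT reviews (Section 10.3.2).

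The SAP also has partial safeguards: visual outlier screening with possible re-assay (8.5), removal of subjects from PK evaluation when significant deviations affect the data (6.2), and reasons given for excluded samples (9.7.1). Re-assay cannot reveal drug that entered the tube at the draw, and the other two need the draw site to be known.

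**Conclusion.** The inconsistency between Sections 7.2 and 7.3.12 is real. It has practical effect on single-lumen lines and on any draw from the drug lumen; with a multi-lumen line both sections can be satisfied. The consequence is a plausible upward bias in peri-infusion concentrations, chiefly Cmax and early AUC. That bias is a risk, not a demonstrated result.

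The documents do not bound its size. The figures of about 1% to 2% and 43% to 109% at 72 µg depend on linear scaling, 10 µL carried over, a 2 to 5 mL sample, and a line concentration equal to one of the two compatibility-test values. They show only that the effect could be trivial or could matter. The point concerns secondary endpoints and is worth correcting because the correction is cheap. It does not touch the primary safety endpoint.

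**What to change.** 1. Reconcile the two sections into one sampling rule by carrying the 7.2 restriction into 7.3.12: PK samples come from a peripheral vein or from a lumen that does not carry AMG 673, and any central draw with the infusion paused is limited to that other lumen. Check that the laboratory manual says the same.
2. Record the draw site for each PK sample on the eCRF.
3. For samples already taken, flag peri-infusion draws made through the drug line where source records identify them. Report Cmax and AUC with and without them, and give the reasons under SAP Section 9.7.1. Blanket exclusion is not workable: nothing shows that the draw site was captured, and it would also discard late samples that are little affected.

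The cost is protocol wording, one data field and one sensitivity analysis. The downside is that subjects with a single-lumen line need peripheral draws, which 7.3.12 already prefers during infusion.

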7.4 Antibody Testing Procedures

Blood samples for antibody testing are to be collected at the time points outlined in the Schedules of Assessments ([Section 7.1](#)) or the measurement of [REDACTED]

[figure not shown]
██████████ Samples testing positive may be further characterized for quantity/titer, isotype, affinity, in vitro neutralizing activity, and presence of immune complexes. Additional blood samples may be obtained to rule out anti-drug antibodies during the study. Subjects who test positive for binding antibodies and have clinical sequelae that are considered potentially related to an ██████████ response may also be asked to return for additional follow-up testing.

Approved

Approved

Approved

7.6 Disease Response

Disease response assessments will be based upon review of cytogenetics, bone marrow aspirates/biopsies, and peripheral blood count.

Response categories are defined as follows ([Appendix E](#) and [Topp et al, 2015](#)):

CR:

- less than 5% blasts in the bone marrow
- absence of blasts with Auer rods
- absence of extramedullary disease
- absolute neutrophil count (ANC) $\geq 1,000/\mu\text{l}$
- platelet count $\geq 100,000/\mu\text{l}$
- independence of red cell transfusions

CRi

- all CR criteria except for incomplete recovery of peripheral blood counts (residual neutropenia [$< 1,000/\mu\text{l}$] or thrombocytopenia [$< 100,000/\mu\text{l}$])

Morphologic leukemia-free state

- less than 5% myeloblasts in the bone marrow
- absence of blasts with Auer rods
- absence of extramedullary disease
- no hematologic recovery required

CRh*

- less than 5% blasts in the bone marrow
- no evidence of disease
- partial recovery of peripheral blood counts: platelet count $> 50,000/\mu\text{l}$, and ANC $> 500/\mu\text{l}$
- no extramedullary disease

Response must be established from a bone marrow sample supplemented with neutrophil and platelet counts.

